2.3 Rationale

The FGF-FGFR signaling pathway plays a critical role in regulating physiologic processes such as embryogenesis, angiogenesis and cell survival. *FGFR* genes are proto-oncogenes and their activation secondary to genomic alterations such as gene amplification, chromosomal translocation, and point mutation can mediate the development and growth of cancers.¹ A rapidly expanding list of cancers with genomic FGFR alterations is provided in Table 1. Therefore, inhibition of the FGF-FGFR signaling pathway presents a viable therapeutic strategy for multiple malignancies. In addition to their role in inhibiting angiogenesis and tumorigenesis, FGFR inhibitors can also ameliorate resistance to other therapies. Inhibition of FGFR has been demonstrated to overcome resistance to endocrine therapy in patients with breast cancers.³¹ They have also been shown to enhance sensitivity of resistant tumors to chemotherapy.³² FGFR inhibitors are purported to be an effective therapeutic option for relapsed tumors that have been treated previously with EGFR or VEGFR inhibitors due to secondary FGFR activation.¹¹

Currently FGFR inhibitors, both selective and non-selective are being evaluated as cancer therapies. Several small molecule tyrosine kinase inhibitors (TKI) have been studied, and they share characteristics as ATP-competitive VEGFR2 inhibitors due to structural similarity of VEGFR and FGFR kinase domains. However, potential toxicities associated with pan-FGFR/VEGFR inhibition have also led to monoclonal antibodies targeting specific FGFRs (e.g. IMC-A1 (Imclone), R3Mab (Genentech)).^{33, 34} Preclinical as well as early clinical studies have demonstrated that genomic FGFR alterations predict sensitivity and response to the use of FGFR inhibitors. Guagnano *et al.* have shown that genetic alterations in FGFR predict sensitivity to BGJ398 (Novartis), a selective pan-FGFR inhibitor.³⁵ Currently, BGJ398 is being evaluated in a Phase 1 study for patients with advanced solid tumors harboring amplifications (*FGFR1/2*) or mutations (*FGFR3*).³⁶ Dovitinib (TKI258, Novartis), a combined FGFR and VEGFR inhibitor, has recently been shown to be effective in patients with *FGFR1* amplified advanced breast cancers.³⁷ Similarly, *FGFR2* amplification in gastric cancers predicted sensitivity to selective FGFR inhibitor AZD4547 (AstraZeneca)³⁸, and this agent is being investigated in a phase-2 trial in patients with advanced gastric adenocarcinoma with *FGFR2* polysomy or amplification^{39, 40}.

We propose to evaluate ponatinib (Takeda), a pan-FGFR inhibitor, in patients with any cancer histology and molecular eligibility with defined genomic *FGFR* alterations. Ponatinib is FDA approved for the treatment of CML and Philadelphia chromosome positive ALL) for

whom no other tyrosine kinase inhibitor (TKI) therapy is indicated.²⁵ In addition to BCR-ABL, it is also a potent inhibitor of FGFR family members and other kinases including KIT, RET, PDGFR α , and FLT3. Gozgit *et al.* have shown ponatinib to be more potent (1 to 2 log scale) than previous FGFR inhibitors with activity across multiple FGFRs (FGFR 1-4) and types of genomic alterations.¹⁷ Also, ponatinib has been shown to have activity against secondary gatekeeper mutations that mediated resistance in tyrosine kinases (e.g. T315I in BCR-ABL; T670I in KIT).²⁵ We and others (Gozgit *et al.*) have shown that ponatinib produces a robust, dose-dependent, growth inhibition across multiple cancer cell lines harboring *FGFR* alterations, compared to wild type FGFR, supporting these findings. **We hypothesize that activating genomic FGFR alterations predict response to ponatinib.** In addition, we hypothesize that activating genomic alterations in *KIT*, *RET*, *PDGFR α* , *ABL1*, *FLT3* will predict response to ponatinib given the activity of this drug in preclinical studies.

To evaluate this, we propose a single arm phase-2 study of ponatinib in patients with any cancer histology and molecular eligibility with activating *FGFR* alterations (amplifications, mutations, translocations) as well as *KIT*, *PDGFR α* , *FLT3*, *RET*, *ABL1* alterations. While enrollment of multiple tumor subtypes facilitates accrual rate of patients with genetic *FGFR* alterations as these are rare, importantly, we can assess whether tumor subtypes with *FGFR* alterations would indeed respond to *FGFR* inhibition. For instance, *BRAF* mutant colon cancers did not show sensitivity to *BRAF* inhibition as melanomas with similar mutation.⁴¹ This was demonstrated to be due to EGFR-mediated reactivation of MAP kinase pathway, and combined EGFR and *BRAF* inhibition was able to improve response.⁴² As yet, no tumor specific context for *FGFR* response has been recognized and our trial could help ascertain if there is any. Further, we can compare primary non-responders versus responders to identify additional pathways that render patients resistant to *FGFR* inhibition despite the presence of an *FGFR* alteration. As stated previously, ponatinib has also been demonstrated to be a potent inhibitor of other kinases altered in cancers including *PDGFR α* , *FLT3*, *RET*, *ABL1* and *KIT*.^{43, 44} Therefore, we plan to evaluate the activity of ponatinib in cancers that harbor genomic alterations in these kinases as a separate cohort.

3. PATIENT SELECTION

3.1 Eligibility Criteria

- 3.1.1 Patients with histologically or cytologically confirmed diagnosis of refractory metastatic solid tumor for whom no other standard treatment options are available.
- 3.1.2 Patients must have tumor suitable for biopsy (as assessed by trained specialists in interventional radiology) and medically fit to undergo a biopsy or surgical procedure; OR archival tumor specimen of biopsied tumor; OR if patients do not have a tumor suitable for biopsy but have another tissue (preferably progressive metastatic site) available for molecular evaluation (*biopsy will be performed through OSU-13053 study or the UM Precision Cancer Study*).

3.1.3 Patients must have activating genomic alterations in *FGFR* (mutations, fusions or amplifications (> 6 copies)) or activating genomic alterations in *KIT*, *PDGFR α* , *RET*, *ABL1* and *FLT3* by any validated CLIA-certified molecular testing (FISH, PCR or sequencing data are acceptable). CLIA validated results from other institutions; diagnostic labs (e.g. foundation medicine) are acceptable.

3.1.4 Patients with solid tumors must have measurable disease (RECIST 1.1), defined as at least one lesion that can be accurately measured in at least one dimension (longest diameter to be recorded for non-nodal lesions and short axis for nodal lesions) as ≥ 20 mm with conventional techniques or as ≥ 10 mm with spiral CT scan, MRI, or calipers by clinical exam. Note: This trial is open only to patients with solid tumors.

3.1.5 Patients older than or equal to 18 years of age (The safety and efficacy of ponatinib in patients less than 18 years of age have not been tested).

3.1.6 ECOG performance status ≤ 1 (Karnofsky $\geq 80\%$, see Appendix A).

3.1.7 Life expectancy of greater than 3 months.

3.1.8 Patients with multiple malignancies remain eligible.

3.1.9 Patients with an inherited cancer syndrome or a medical history suggestive of an inherited cancer syndrome remain eligible.

3.1.10 Patients must have controlled blood pressure with a systolic blood pressure < 140 mmHg and diastolic < 90 mmHg (for patients with an elevated initial BP reading (hypertensive range), a repeat measurement at least 2 minutes later should be performed, and the two readings should be averaged to obtain a BP reading). Any hypertensive at-home blood pressure reading will be confirmed in clinic. Patients on anti-hypertensive medications are eligible, if blood pressure is controlled. Study drug dosing will be interrupted for any reading $\geq 160/100$, as outlined in management table in Section 6 of the protocol.

3.1.11 Ponatinib can cause fetal harm when administered to a pregnant woman based on its mechanism of action and findings in animals. For this reason women of child-bearing potential and men must agree to use adequate contraception (hormonal or barrier method of birth control; abstinence) prior to study entry and through 4 months after the end of treatment. For females of childbearing potential, a negative pregnancy test must be documented prior to registration.

3.1.12 Patients must have normal organ and marrow function as defined below:

- Absolute neutrophil count $\geq 1,500/\text{mcL}$
- Platelets $\geq 75,000/\text{mcL}$
- Total bilirubin $\leq 1.5 \times$ upper limit of normal (ULN), unless due to Gilbert's syndrome (< 5 if liver involvement with primary tumor)
- Serum lipase and amylase $\leq 1.5 \times$ ULN

- AST(SGOT)/ALT(SGPT) $\leq 2.5 \times$ institutional upper limit of normal
- LVEF $\geq 50\%$ by ECHO or MUGA
- Serum creatinine ≤ 1.5 mg/dL *OR* calculated creatinine clearance (Cockcroft-Gault formula) ≥ 60 mL/min *OR* 24-hour urine creatinine clearance ≥ 60 mL/min

3.1.13 Patient has the ability to swallow oral medication and keep a pill diary

3.1.14 Ability to understand and the willingness to sign a written informed consent document.

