11.1.2 Disease Parameters

Measurable disease. Measurable lesions are defined as those that can be accurately measured in at least one dimension (longest diameter to be recorded) as ≥ 20 mm by chest x-ray or as ≥ 10 mm with CT scan, MRI, or calipers by clinical exam. All tumor measurements must be recorded in millimeters (or decimal fractions of centimeters).

Note: Tumor lesions that are situated in a previously irradiated area may be considered measurable.

Malignant lymph nodes. To be considered pathologically enlarged and measurable, a lymph node must be ≥ 15 mm in short axis when assessed by CT scan (CT scan slice thickness recommended to be no greater than 5 mm). At baseline and in follow-up, only the short axis will be measured and followed.

Non-measurable disease. All other lesions (or sites of disease), including small lesions (longest diameter <10 mm or pathological lymph nodes with ≥ 10 to <15 mm short axis), are considered non-measurable disease. Bone lesions, leptomeningeal disease, ascites, pleural/pericardial effusions, lymphangitis cutis/pulmonitis, inflammatory breast disease, and abdominal masses (not followed by CT or MRI), are considered as non-measurable.

Note: Cystic lesions that meet the criteria for radiographically defined simple cysts should not be considered as malignant lesions (neither measurable nor non-measurable) since they are, by definition, simple cysts.

‘Cystic lesions’ thought to represent cystic metastases can be considered as measurable lesions, if they meet the definition of measurability described above. However, if non-cystic lesions are present in the same patient, these are preferred for selection as target lesions.

Target lesions. All measurable lesions up to a maximum of 2 lesions per organ and 5 lesions in total, representative of all involved organs, should be identified as **target**

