11.1.4 Response Criteria

11.1.4.1. Evaluation of Target Lesions

Complete Response (CR): Disappearance of all target lesions. Any pathological lymph nodes (whether target or non-target) must have reduction in short axis to <10 mm.

Partial Response (PR): At least a 30% decrease in the sum of the diameters of target lesions, taking as reference the baseline sum diameters.

Progressive Disease (PD): At least a 20% increase in the sum of the diameters of target lesions, taking as reference the smallest sum on study (this includes the baseline sum if that is the smallest on study). In addition to the relative increase of 20%, the sum must also demonstrate an absolute increase of at least 5 mm. (Note: the appearance of one or more new lesions is also considered progression).

Stable Disease (SD): Neither sufficient shrinkage to qualify for PR nor sufficient increase to qualify for PD, taking as reference the smallest sum diameters while on study.

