11.1.4.2. Evaluation of Non-Target Lesions

Complete Response (CR): Disappearance of all non-target lesions and normalization of tumor marker level. All lymph nodes must be non-pathological in size (<10 mm short axis).

Note: If tumor markers are initially above the upper normal limit, they must normalize for a patient to be considered in complete clinical response.

Non-CR/Non-PD: Persistence of one or more non-target lesion(s) and/or maintenance of tumor marker level above the normal limits.

Progressive Disease (PD): Appearance of one or more new lesions and/or *unequivocal progression* of existing non-target lesions. *Unequivocal progression* should not normally trump target lesion status. It must be representative of overall disease status change, not a single lesion increase.

Although a clear progression of “non-target” lesions only is exceptional, the opinion of the treating physician should prevail in such circumstances, and the progression status should be confirmed at a later time by the review panel (or Principal Investigator).

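### Eligibility accepts lymph nodes of 10 mm short axis as measurable disease, but Section 11.1.2 requires 15 mm, so a patient can enter with no target lesion and no route to PR and still count in the response denominator

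*Combined protocol and SAP*

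**What the plan says.** **Eligibility.** Section 3.1.4 asks for measurable disease under RECIST 1.1 and then writes out its own definition. At least one lesion must be measurable, with the "short axis for nodal lesions) as ≥ 20 mm with conventional techniques or as ≥ 10 mm with spiral CT scan"; MRI and calipers share the 10 mm limit. Nodes get no separate size limit.

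**Response assessment.** Section 11.1.2 says that to be measurable "a lymph node must be ≥ 15 mm in short axis when assessed by CT scan", and its list of non-measurable disease includes "pathological lymph nodes with ≥ 10 to <15 mm short axis". Target lesions are drawn from "All measurable lesions up to a maximum of 2 lesions per organ and 5 lesions in total". Section 11.1.3 adds a third version: it treats superficial palpable nodes as measurable from 10 mm diameter by calipers.

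**Response criteria.** PR (Section 11.1.4.1) is "At least a 30% decrease in the sum of the diameters of target lesions". For CR the same section states: "Any pathological lymph nodes (whether target or non-target) must have reduction in short axis to <10 mm". Section 11.1.4.2 has a matching nodal condition for non-target CR: "All lymph nodes must be non-pathological in size (<10 mm short axis)".

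**Who counts.** Section 11.1.1 limits evaluability for objective response to patients with measurable disease at baseline. Section 12.1(a) makes every eligible patient with at least one dose evaluable. Section 12.5.2 puts all eligible patients in the main response analysis (with a possible exception for those never treated) and scores unassessable patients as failures.

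**The concern.** Two sections of current text use different nodal limits for the same term. Section 3.1.4 decides who enters; Section 11.1.2 decides what can be followed for response. A patient whose sole qualifying lesion is a 10 to <15 mm node falls between them.

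The primary endpoint is a response count in a small cohort. In Cohort A, one response separates stopping from continuing at stage 1 (0 versus 1 of 10) and failure from success at the end (3 versus 4 of 30). A patient who cannot reach PR lowers the chance of success. A patient who reaches CR on a small nodal change raises the chance of a false success. Which error occurs depends on the section the site follows.

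**Working it through.** **1. The path of one patient.** Take a patient whose only qualifying lesion is a 12 mm node on CT.

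- Section 3.1.4: 12 ≥ 10, so eligible.
- Section 11.1.2: 12 < 15, so the node is non-measurable and there is no target lesion.
- Section 11.1.4.1: PR is defined only on target lesions. The table for non-measurable disease in Section 11.1.4.3 has no PR row. CR is still available there.
- Section 11.1.1: not evaluable for objective response.
- Sections 12.1(a) and 12.5.2: in the denominator once dosed.

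**2. CR against PR if the node is used as a target lesion.** For a sole node of baseline size b mm, PR needs a size of at most 0.7b and CR needs a size below 10. CR is reached before PR when 0.7b < 10, that is b < 10/0.7 = 14.3 mm.

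| Baseline (mm) | PR at or below (mm) | Fall if read at 9 mm |
|---|---|---|
| 10 | 7.0 | 10% |
| 11 | 7.7 | 18.2% |
| 12 | 8.4 | 25% |
| 13 | 9.1 | 30.8% |
| 14 | 9.8 | 35.7% |
| 15 | 10.5 | 40% |

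With whole-millimetre readings, the first value under 10 is 9, so the anomaly shows at 10, 11 and 12 mm (9/0.7 = 12.9). With finer readings it extends to 14.3 mm: a 14 mm node reaches 10 mm after a fall of 4/14 = 28.6%. At the 15 mm limit it disappears, because CR needs a fall of more than 5/15 = 33.3% and PR needs 30%.

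**3. The plan's own figures.** Inputs from Section 12.2: 10 then 20 patients; continue with at least 1 response; success with at least 4 of 30; p0 = 0.05, p1 = 0.20. The probability of success is

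P(p) = Σ over x = 1 to 10 of P(X1 = x) × P(X2 ≥ 4 − x), with X1 ~ Bin(10, p) and X2 ~ Bin(20, p).

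P(0.20) = 81.4%, which meets the stated 80%. P(0.05) = 5.13%, marginally above the stated 5%; that is a separate matter. The formula leaves out the special branch in Section 12.2 for ten amplification-only patients with no response.

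**4. Patients who cannot respond (number assumed).** If on average k of 30 cannot respond, the effective rate is 0.20 × (1 − k/30).

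| k | Effective rate | Power |
|---|---|---|
| 0 | 0.2000 | 81.4% |
| 1 | 0.1933 | 79.3% |
| 2 | 0.1867 | 77.1% |
| 3 | 0.1800 | 74.6% |

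**5. False CRs (share and chance assumed).** If 1 in 30 patients has such a node and a chance q of a false CR, the effective null rate is 0.05 × 29/30 + q/30.

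| q | Effective null rate | Type I error |
|---|---|---|
| none affected | 0.0500 | 5.1% |
| 0.1 | 0.0517 | 5.7% |
| 0.3 | 0.0583 | 8.0% |
| 0.5 | 0.0650 | 10.9% |

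**The case against.** The strongest reply is that this is a drafting slip with safeguards around it. Section 3.1.4 names RECIST 1.1, as does Section 11.1, so a site may apply the 15 mm limit anyway. Section 11.1.2 governs target selection, so using a 12 mm node as a target lesion would breach it. Responses need confirmation (Sections 11.1 and 11.1.4.3), and an independent expert reviews all of them (Section 11.1.7). For external sites, Section 4.2 has eligibility verified centrally against source documents. Entry is limited to refractory metastatic disease, where a sole small node may be rare.

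Much of this stands, and it rules out several stronger readings that a reader might infer:

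- *These patients cannot respond at all.* Only PR is closed. CR by the non-target route remains.
- *A 1 mm change gives a CR.* This needs a sole node at exactly 10 mm, no new lesions, no other remaining disease, normal markers where relevant, and confirmation.
- *Sites will admit such patients.* The text permits it, but the eligibility checklist is in a forms packet outside these documents, so the limit it carries is unknown.
- *The denominator is settled.* Section 11.1.1 conflicts with Sections 12.1(a) and 12.5.2.
- *Such patients add nothing.* They still contribute to toxicity, PFS, OS and clinical benefit.

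The safeguards do not remove the problem. The RECIST label is followed by an explicit definition with different numbers, and central verification checks the written criterion. Independent review comes at study completion, too late to undo enrolment or a stage 1 decision. It covers responses, so it does not help a patient for whom PR was never available. The low CR limit also applies by the non-target route, where no breach of Section 11.1.2 is needed.

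**Conclusion.** The contradiction is literal and should be corrected. Sections 3.1.4, 11.1.2 and 11.1.3 give different nodal limits for measurable disease. An eligible patient can therefore have no target lesion and no route to PR, with opposite answers on whether that patient counts. If Section 3.1.4 is also used to choose target lesions, CR becomes easier than PR for a sole node below 14.3 mm.

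The size is uncertain. The documents give neither the share of patients affected nor the chance of a false CR, so the figures above are illustrations. Under them, an average of one non-responding patient in 30 takes power just below the 80% target. One patient in 30 with an even chance of a false CR roughly doubles the type I error. The power figures treat the affected patients as unable to respond, so they overstate the loss to the extent that non-target CRs occur. If no such patient enrols, nothing changes.

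**What to change.** In Section 3.1.4 and the eligibility checklist, replace the common limit with those of Section 11.1.2: non-nodal lesions at least 10 mm by CT, MRI or calipers, or 20 mm by chest x-ray; lymph nodes at least 15 mm short axis by CT. Align the palpable-node wording in Section 11.1.3 with the same nodal limit; otherwise correcting Section 3.1.4 alone leaves a conflict with that section.

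The cost is a wording change in two sections and the checklist. Sample size and decision rule stay as they are. The downside is that the rare patient with only 10 to <15 mm nodal disease is no longer eligible; Section 11.1.1 already treats that patient as not evaluable for response.

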3.2 Exclusion Criteria

3.2.1 Patients with hematological malignancies.

3.2.2 Patients who have not received any prior treatment.

3.2.3 Patients with known ponatinib-resistant gene alterations

- PDGFRA D842V mutation
- cKIT D816V mutation
- FLT3 D835V/Y/H/F or Y842C mutations
- FGFR3 K652E mutation

3.2.4 Major surgery (e.g. thoracic, abdominal, vascular, neurosurgery) within 28 days prior to registration on study.

3.2.5 History of acute pancreatitis within one year of study entry or history of chronic pancreatitis.

3.2.6 History of alcohol abuse

3.2.7 Have uncontrolled hypertriglyceridemia (triglycerides >450 mg/dL).

3.2.8 Patients who are receiving any other investigational agents.

3.2.9 Patients with history of clinically significant bleeding disorder.

3.2.10 Pregnant women are excluded from this study because ponatinib can affect embryo-fetal development. Because there is an unknown but potential risk for adverse events in nursing infants secondary to treatment of the mother with ponatinib breastfeeding must be discontinued.

3.2.11 Patients who are incarcerated are not eligible.

3.2.12 Patients with any history of arterial thromboembolic disease. *Any patient with a history of MI, stroke, TIA, unstable angina or peripheral vascular disease will not be eligible.*

3.2.13 Patients with history of recurrent venous thromboembolism (deep venous thrombosis or pulmonary embolism) or history of venous thromboembolism within 6 months prior to registration on study will not be eligible

3.2.14 Patients with history of active hepatitis B or C infection or chronic hepatitis with Child Pugh B or C hepatic dysfunction.

3.2.15 Patients with prolonged corrected QT interval, defined as QTc >450 msec

3.2.16 Use of antiplatelet agents other than low-dose aspirin as described in the protocol.

3.2.17 GI bleed within 30 days prior to registration on study .

3.2.18 History of allergic reactions attributed to compounds of similar chemical or biologic composition to ponatinib.

3.2.19 Patients with history of atrial arrhythmia (requiring any anti-arrhythmic therapy) or patients with any history of ventricular arrhythmia are excluded

3.2.20 Clinically significant, uncontrolled intercurrent illness including, but not limited to:

- Symptomatic or active infection
- Uncontrolled hypertension (Diastolic blood pressure > 90 mm Hg; Systolic >140 mm Hg). Patients with hypertension should be under treatment on study entry to effect blood pressure control.
- Psychiatric illness/social situations that would limit compliance with study requirements.

3.2.21 Patients with history of congestive heart failure are excluded.

3.2.22 HIV-positive patients on combination antiretroviral therapy are ineligible because of the potential for pharmacokinetic interactions with ponatinib.

